**Figure 1: Study Schema: Eligibility Evaluation and Initial Therapy**

### **3.2 PHASE II STUDY DESIGN FOR HIGH-DOSE METHOTREXATE WITH LEUCOVORIN RESCUE AND RITUXIMAB**

Induction treatment cycles with rituximab, high-dose methotrexate and leucovorin will be administered every 2 weeks for 6 cycles. Two additional consolidation cycles of high-dose methotrexate without rituximab will be administered at 4 weeks and 8 weeks following completion of the combined therapy.

MRI will be repeated at the end of cycles 2, 4, 6, and 8, and additionally as clinically indicated. At the time of first evidence for complete tumor response by MRI criteria, FDG-PET scan and EBV DNA assessments of the blood and CSF will be repeated. If there is not a complete response by end of cycle 6, patients will be categorized as treatment failures and will not receive the two additional high-dose methotrexate doses. At end of treatment, restaging by MRI will be performed once every 2 months x 3; then once every 3 months x 6; then once every 6 months x 2; then as clinically indicated or annually up to year 5. After this period, clinical evaluations may continue and restaging

performed if clinical suspicion of CNS pathology. Additionally, FDG-PET scan will be repeated as outlined in section 3.8.4.2. (See also Appendix 3).

### **3.3 DRUG ADMINISTRATION: HIGH-DOSE METHOTREXATE WITH LEUCOVORIN RESCUE AND RITUXIMAB, AND HAART**

- 3.3.1 Review all concomitant medications prior to day 1 of each cycle. Discontinue any drug that may potentially interact with methotrexate elimination.
- 3.3.2 Rituximab
  - 3.3.2.1 Rituximab 375 mg/m^2 IV day 1 of each cycle prior to administration of high-dose methotrexate.
  - 3.3.2.2 Administer the first dose at an initial rate of 50 mg/hr; if hypersensitivity reactions and/or infusion-related events do not occur, the infusion rate may be increased in increments of 50 mg/hour every 30 minutes to a maximum infusion rate of 400 mg/hour. Subsequent rituximab infusions may be administered at an initial infusion rate of 100 mg/hour; the rate of infusion may be increased every 30 minutes in increments of 100 mg/hour as tolerated to a maximum infusion rate of 400 mg/hour. Rituximab must be diluted prior to injection (See Section 9.1). No other drugs should be added or administered in the same IV line as rituximab.
  - 3.3.2.3 Administer acetaminophen 650 mg PO 30-60 minutes prior to starting rituximab administration (May hold if a patient is unable to swallow oral medications).
  - 3.3.2.4 Administer diphenhydramine 25 – 50 mg IV 10- 30 minutes prior to starting rituximab administration.
  - 3.3.2.5 Consider holding antihypertensive medication during the 12-hour period prior to dosing rituximab, and on the day of rituximab administration.
- 3.3.3 Intravenous fluid and urine alkalization
  - 3.3.3.1 On Day 1, 12 – 18 hours before the anticipated start of methotrexate, start IV hydration containing sodium bicarbonate (NaHCO3) to alkalinize a patient's urine to pH  $\geq$ 7.0, but  $\leq$  8.0 at a rate that achieves a urine output  $\geq$ 100 mL/hr (recommended start by 6PM local time on day 1). See Table below for options recommended to initially produce an alkaline urine.
    - 3.3.3.1.1 Order q 6-hour urine pH measurements (e.g., 0000, 0600, 1200, 1800) and strict urine output monitoring to start with initiation of IV hydration. Record urine output hourly until urine output is  $>$  100 cc/hour, then at least every four hours.
    - 3.3.3.1.2 Nursing staff should notify a medically responsible individual (investigator or staff on-call) for urine output  $<$ 100 mL/hour or urine pH  $<$ 7 or  $>$ 8.
  - 3.3.3.2 Urine alkalinization to pH  $\geq$ 7.0 to  $\leq$ 8.0 and urine output  $\geq$ 100 mL/hour often initially requires more NaHCO3 and more rapid hydration rates than will be required to maintain either or both parameters after they are achieved.
  - 3.3.3.2.1 The amount of sodium bicarbonate added to intravenously administered fluids should produce a solution with sodium content not greater than the concentration of sodium in 0.9% Sodium Chloride Injection ( $\leq$ 154 mEq/L).

3.3.3.2.2 Recommendations for initially achieving urine alkalinization to pH  $\geq 7.0$  to  $\leq 8.0$  and urine output  $\geq 100$  mL/hour:

Fluid	Administration Rate	Sodium Bicarbonate Content (per 1,000 mL)
0.45%NS	150 – 250 mL/h	50 – 75 mEq
0.2%NS		100 – 125 mEq
D5W/0.45%NS		50 – 75 mEq
D5W/0.2%NS		100 – 125 mEq
D5W		150 mEq

D5W: 5% Dextrose Injection, USP

NS: Sodium Chloride Injection, USP

3.3.3.3 In cases where the investigators feel that a patient can reliably maintain adequate hydration orally, intravenous hydration may be discontinued after the serum methotrexate level is  $<0.5$  mcMol/L.

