Encouraging data on the utility of unlabeled rituximab in AIDS-unrelated PCNSL has been reported in small studies. Since CNS lymphoma has a predisposition for perivascular infiltration that disrupts the blood brain barrier, greater anticancer agent penetration into areas of the brain affected by tumor are seen when compared to surrounding normal brain, as shown in biopsy and autopsy specimen in studies addressing this. Indeed, there is mounting clinical experience that rituximab can be useful in primary brain lymphoma when administered intravenously. In small studies of refractory PCNSL, responses have been seen in the majority of treated patients who received rituximab monotherapy or rituximab in combination with cytotoxic agents. Although reports that rituximab monotherapy in previously treated refractory-relapsed PCNSL results in clinical and radiographic responses suggests that rituximab can penetrate into areas of bulky disease in the brain, there is insufficient data to know with certainty what the overall contribution of rituximab is in the combination chemotherapy setting. However, PCNSL experts have supported its clinical trials development. The Cancer and Acute Leukemia Group B trial 50202 entitled “Intensive Chemotherapy and Immunotherapy in Patients with Newly Diagnosed Primary CNS Lymphoma” is a multi-institutional study further investigating rituximab combining it with high-dose methotrexate and temozolomide. Thus, there is well-established precedent for investigating the use of rituximab in PCNSL in the HIV unrelated setting. Likewise, rituximab may be a promising agent in AIDS-related PCNSL as

articulated above. The core regimen in this protocol will thus investigate the use of leucovorin protected high-dose methotrexate with rituximab and HAART.

Rituximab will be omitted from cycles 7 and 8. The rationale for this is that only patients who have achieved a complete response will receive the additional two cycles. Therefore, it is assumed that rituximab penetration into the area previously affected by obvious tumor will become insufficient due to improved blood-brain barrier integrity. However, it may be beneficial to administer additional high-dose methotrexate cycles with increased dose-intervals in order to help prevent early tumor recurrence while allowing for additional time for greater immunologic recovery.

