### Arms

Number	Name	Description
1	Single arm	Induction treatment cycles with rituximab, high-dose methotrexate and leucovorin will be administered every 2 weeks for 6 cycles. Two additional consolidation cycles of high-dose methotrexate without rituximab will be administered at 4 weeks and 8 weeks following completion of the combined therapy.

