### Day 1 of each cycle:

1. Review all concomitant medications prior to day 1 of each cycle. Discontinue any drug that would have interaction with methotrexate excretion. See list below. No filgrastim within 24 hours before methotrexate administration.
2. Rituximab 375 mg/m^2
3. Start IV fluid hydration by 18:00, using one of the protocol specified alkalinized IVF order sets in CRIS for 06-C-0051
4. Order q6 hour urine pH  $\geq$  7.0 (00:00, 6:00, 12:00, 18:00) and **STRICT URINE OUTPUT** monitoring record urine output every hour
5. Draw the following blood work until methotrexate level is < or equal to 0.05 mcmol/L:
  - a. Hepatic panel every other day
  - b. CBC/Diff, Chem 7 daily

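### Section 3.3.2.1 and Appendix 9 order rituximab on day 1 of each cycle, while section 1.2.4.3, the arm definition and section 3.2 omit it from cycles 7 and 8

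*Combined protocol and SAP*

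**What the plan says.** Three places define the regimen, and they agree.

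- Section 1.2.4.3: "Rituximab will be omitted from cycles 7 and 8". The reason given is that only complete responders go on to these cycles, and the drug is assumed to reach the former tumour area poorly once the blood-brain barrier has recovered.
- Section 2.4, Arms: six induction cycles of rituximab, high-dose methotrexate and leucovorin, and then "Two additional consolidation cycles of high-dose methotrexate without rituximab will be administered at 4 weeks and 8 weeks" after the combined therapy.
- Section 3.2: the same statement as the arm definition. It adds "If there is not a complete response by end of cycle 6, patients will be categorized as treatment failures", and those patients do not receive the last two methotrexate doses.

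Two places tell staff what to give.

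- Section 3.3.2.1: rituximab 375 mg/m² "IV day 1 of each cycle prior to administration of high-dose methotrexate".
- Appendix 9, under the heading "Day 1 of each cycle", item 2: rituximab 375 mg/m².

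Neither of these two carries a cycle limit.

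**The concern.** The omission of rituximab from consolidation is a deliberate design choice with a stated reason, and the drug order does not reflect it. Section 3.3 and Appendix 9 are the texts from which treatment is ordered and given. The protocol has no separate administration section or checklist for consolidation, so staff must use these same texts for methotrexate and leucovorin in cycles 7 and 8. The rituximab line stands there without qualification.

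What is at stake is uniform exposure among complete responders, the only patients who reach cycles 7 and 8. Staff who follow section 3.2 give no rituximab in those cycles; staff who follow 3.3.2.1 literally give up to two further doses. Each course also departs from some approved text: giving the drug departs from the arm definition, and withholding it departs from the letter of 3.3.2.1. Section 8.1.8 counts any departure from the approved protocol as a deviation.

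**Working it through.** **1. Do the consolidation courses count as cycles?** Yes. Section 3.2 says "MRI will be repeated at the end of cycles 2, 4, 6, and 8", section 1.2.4.3 refers to cycles 7 and 8 by number, and the evaluation table in Appendix 3 has rows for Cycle 7 and Cycle 8.

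**2. How is the phrase used nearby?** Section 3.3.1 says "Review all concomitant medications prior to day 1 of each cycle". Item 1 of the same Appendix 9 list repeats that review and adds "Discontinue any drug that would have interaction with methotrexate excretion". This check is needed whenever methotrexate is given, including cycles 7 and 8. In those lines, then, each cycle covers all eight, and the rituximab line next to them uses the same words.

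**3. Is there an exception elsewhere in the dosing text?** The rest of 3.3.2 covers infusion rate, premedication and antihypertensives. Section 3.4.1 covers infusion reactions. Section 9.1 covers supply, preparation and administration of the drug. None of them exempts cycles 7 and 8.

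**4. Dose count for a patient who completes cycle 8.** Inputs: 375 mg/m² per dose (3.3.2.1), 6 induction cycles and 2 consolidation cycles (2.4 and 3.2). The protocol states no cumulative rituximab dose, so there is no figure of its own to reproduce here.

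| Reading | Doses | Cumulative dose |
|---|---|---|
| Regimen as defined (1.2.4.3, 2.4, 3.2) | 6 | 6 × 375 = 2,250 mg/m² |
| Literal order (3.3.2.1, Appendix 9) | 6 + 2 = 8 | 8 × 375 = 3,000 mg/m² |

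Difference: 3,000 − 2,250 = 750 mg/m², and 750 / 2,250 = 33%.

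**5. Does the statistical design depend on this?** No. Section 6.1.3 states 88% power for 15 patients with a one-sided 0.1-level exact binomial test of 30% against 65%. Requiring at least 8 successes in 15 gives an exact alpha of 0.0500 and power of 0.887, which agrees with the stated figure. (At least 7 successes would give alpha 0.131, above the limit.) The number of rituximab doses does not enter this calculation.

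**The case against.** The strongest reply is that the protocol already settles the matter. The exclusion appears three times, once with a reason and once directly before section 3.3. Line 3.3.2.1 is a general statement of dose, route, day and order relative to methotrexate, and on an ordinary reading a specific rule governs a general one. Section 3.2 describes the first six cycles as the rituximab-containing ones and calls them the combined therapy; the title of Appendix 9 likewise speaks of rituximab combined with methotrexate. Each cycle could therefore mean each cycle that contains rituximab. Appendix 9 also sends fluids and methotrexate through trial-specific order sets, and the documents do not show how rituximab is set up there.

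Most of this stands. A reader might infer from step 2 of the working that the phrase cannot be read as induction only. That goes too far: the literal reading is available and fits the neighbouring lines, but section 3.2 makes the narrower one reasonable. The reply does not remove the mismatch itself. The order as worded still differs from the regimen, and a checklist used at the bedside should not depend on the reader recalling another section.

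**Conclusion.** The inconsistency is real and minor. Two operative dosing texts omit a limit that three other places state. The size that follows from the documents is per patient: up to 8 doses instead of 6 (up to 750 mg/m², or 33%, more) for someone who completes cycle 8 and is dosed by the literal order. The actual excess may be zero, because section 3.2 makes the intent clear.

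Three stronger conclusions are tempting and are not supported.

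- A reader might infer that the extra doses would harm patients or alter the two-year result. The documents do not show this. The excess treatment-related mortality described in section 1.2.4.3 arose when rituximab was added to CHOP, a different regimen.
- A reader might multiply two doses by the planned 15 patients to get a cohort total. The documents give no complete-response rate for this regimen in this disease. The rates quoted in section 1.2.3 come from other regimens in HIV-unrelated lymphoma. Any such total would also assume that section 3.2 is overlooked every time.
- A reader might infer that the trial's statistical design is compromised. Sample size, alpha and power do not depend on the point.

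**What to change.** In section 3.3.2.1, and in Appendix 9, day 1 list, item 2, replace the timing with: *day 1 of cycles 1–6 only; omit rituximab in cycles 7 and 8*. The other day 1 instructions, including the methotrexate-interaction review, should continue to apply to all eight cycles.

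The cost is two one-line wording changes. No patients, visits, procedures or analyses are added, and the regimen itself does not change.

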### **3.4 TREATMENT MODIFICATIONS: HIGH-DOSE METHOTREXATE WITH LEUCOVORIN RESCUE AND RITUXIMAB**

3.4.1 Rituximab

3.4.1.1 For infusion related events or hypersensitivity reactions, the infusion rate should be slowed (e.g. for moderate flu-like symptoms of fever, chills, rigors; other infusion related reactions such as nausea, urticaria, pruritus, rash, fatigue, headache) or infusion of the drug should be interrupted or discontinued as clinically indicated (e.g. for reactions such as angioedema, hypotension, bronchospasm); following appropriate treatment and/or resolution of the reaction(s), administration of rituximab may be reinitiated at a slower infusion rate (one-half the previous infusion rate), and the rate of infusion may be incrementally increased as tolerated.

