#### 3.6.1.2 Administer the first dose at an initial rate of 50 mg/hr; if hypersensitivity

reactions and/or infusion-related events do not occur, the infusion rate may be increased in increments of 50 mg/hour every 30 minutes to a maximum infusion rate of 400 mg/hour. Subsequently, rituximab infusions may be administered at an initial infusion rate of 100 mg/hour; the rate of infusion may be increased every 30 minutes in increments of 100 mg/hour as tolerated to a maximum infusion rate of 400 mg/hour. Rituximab must be diluted prior to injection (See Section 9.1). No other drugs should be added or administered in the same IV line as rituximab.

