9.1.2.1 Hypersensitivity Reaction

9.1.2.2 Angioedema

9.1.2.3 Bronchospasm

9.1.2.4 Hypotension

9.1.2.5 Cardiac arrhythmia

9.1.2.6 Rash

9.1.2.7 Headache

9.1.2.8 Pruritus

9.1.2.9 Fatigue

9.1.2.10 Severe infusion reaction

9.1.2.11 Fatal reactions within 24 hours after administration

9.1.2.12 80% of fatal infusion reactions occurred in association with the first infusion

9.1.2.13 After an infusion reaction complex including 1 or more:

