#### 9.1.5.3 First Infusion

9.1.5.3.1 The rituximab solution for infusion should be administered intravenously at an initial rate of 50 mg/h (25 mL/h). Rituximab should not be mixed or diluted with other drugs. If hypersensitivity or infusion reactions do not occur, escalate the infusion rate in 50 mg/h (25 mL/h) increments every 30 minutes, to a maximum of 400 mg/h (200 mL/h). If hypersensitivity (non-IgE-mediated) or an infusion reaction develops, the infusion should be temporarily slowed or interrupted. The infusion can continue at one-half the previous rate upon improvement of patient symptoms.”

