#### 9.1.5.4 Subsequent Infusions

9.1.5.4.1 If the patient tolerated the first infusion well, subsequent rituximab infusions can be administered at an initial rate of 100 mg/h (50 mL/h), and increased by 100 mg/h (50 mL/h) increments at 30-minute intervals, to a maximum of 400 mg/h (200 mL/h) as tolerated. If the patient did not tolerate the first infusion well, follow the guidelines under First Infusion.

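### Sections 3.3.2.2 and 3.6.1.2 allow every later rituximab infusion to start at 100 mg/h, whereas section 9.1.5.4.1 sends patients who tolerated the first infusion poorly back to a 50 mg/h start

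*Combined protocol and SAP*

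**What the plan says.** Rituximab infusion rates are given in three places.

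- **Section 3.3.2.2 (methotrexate regimen).** The first dose starts at 50 mg/h and rises in 50 mg/h steps every 30 minutes, provided no hypersensitivity or infusion-related event occurs. For later doses: "Subsequent rituximab infusions may be administered at an initial infusion rate of 100 mg/hour", with 100 mg/h steps as tolerated up to 400 mg/h.
- **Section 3.6.1.2 (dose-dense rituximab).** The first dose is handled in the same way, followed by: "Subsequently, rituximab infusions may be administered at an initial infusion rate of 100 mg/hour".
- **Section 9.1.5 (pharmaceutical information).** Section 9.1.5.3.1 sets the first infusion at a 50 mg/h start with 50 mg/h steps. Section 9.1.5.4.1 allows a 100 mg/h start at later infusions on condition that the first was well tolerated. It then adds: "If the patient did not tolerate the first infusion well, follow the guidelines under First Infusion".

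Two other places bear on the point. Section 3.4.1.1 covers slowing, interrupting or stopping an infusion after a reaction, and restarting at half the previous rate. The Day 1 checklist in Appendix 9, which serves the methotrexate regimen, lists the rituximab dose without a rate.

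**The concern.** The dosing sections are the ones staff work from when writing an order. They give an unconditional permission where the pharmaceutical section gives a conditional one. A patient who reacted at the first infusion could be started at the next one at twice the rate that section 9.1.5.4.1 directs, with staff still inside sections 3.3.2.2 or 3.6.1.2.

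Such patients can stay on rituximab. Section 3.4.1.1 allows treatment to resume after reactions that include angioedema, hypotension and bronchospasm, and section 3.5 does not list infusion reactions among its named reasons for discontinuing, although section 3.4.1.1 does permit stopping. In the dose-dense regimen the second infusion follows two days after the first (Days 1 and 3). Under section 3.1.1 that cohort can include patients with ECOG performance status 4 or class III heart failure unresponsive to treatment.

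On severity, the toxicity list in section 9.1.2 states: "80% of fatal infusion reactions occurred in association with the first infusion". Up to 20% (100% − 80%) therefore did not. The protocol does not say how many of those followed an earlier reaction, or at what rate, so this figure is context only.

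**Working it through.** The plan states no figure to reproduce here. The check is a comparison of the text, followed by simple infusion arithmetic.

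**Step 1: the rules for a patient who tolerated the first infusion poorly.**

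| Section | Starting rate at the next infusion | Depends on first-infusion tolerance? |
|---|---|---|
| 3.3.2.2 | 100 mg/h permitted | No |
| 3.6.1.2 | 100 mg/h permitted | No |
| 9.1.5.4.1 with 9.1.5.3.1 | 50 mg/h directed | Yes |
| 3.4.1.1 | None set; covers restarting after a reaction | Not applicable |
| Appendix 9, Day 1 | None set; dose only | Not applicable |

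**Step 2: does other wording in the dosing sections supply the condition?** The tolerance phrase in 3.3.2.2 and 3.6.1.2 attaches to the later increments and does not reach the starting rate. In the same paragraphs, escalation of the first dose is expressly conditional on the absence of a reaction, and the later-infusion start carries no such condition. Both sections refer to section 9.1, but in the sentence about dilution.

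**Step 3: size of the difference.** Each rate is held for 30 minutes and then raised by the stated step.

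- First 30 minutes: 100 × 0.5 = 50 mg, against 50 × 0.5 = 25 mg.
- First hour with full escalation: 50 + 200 × 0.5 = 150 mg, against 25 + 100 × 0.5 = 75 mg.
- First two hours with full escalation: 50 + 100 + 150 + 200 = 500 mg, against 25 + 50 + 75 + 100 = 250 mg.

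Body surface area is not given, so 1.6 to 2.0 m² is assumed. At 375 mg/m² the dose is 600 to 750 mg. The first 30 minutes then deliver 50/600 = 8.3% to 50/750 = 6.7% of the dose, against 25/600 = 4.2% to 25/750 = 3.3%.

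**Step 4: the permitted start compared with the rate at which the patient reacted.** The restart rate is half the reaction rate (section 3.4.1.1).

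| Reaction at (mg/h) | Restart (mg/h) | 100 ÷ reaction rate | 100 ÷ restart rate |
|---|---|---|---|
| 50 | 25 | 2.0 | 4.0 |
| 100 | 50 | 1.0 | 2.0 |
| 150 | 75 | 0.67 | 1.33 |
| 200 | 100 | 0.5 | 1.0 |
| 250 to 400 | 125 to 200 | 0.4 to 0.25 | 0.8 to 0.5 |

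The permitted start is at or above the reaction rate only if the reaction came at 50 or 100 mg/h.

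**Step 5: how often it can arise.** The methotrexate regimen has six rituximab cycles, so 6 − 1 = 5 later infusions. The dose-dense regimen has six doses (Days 1, 3, 5, 8, 15 and 21), so again 6 − 1 = 5. A patient who moves to dose-dense rituximab under section 3.5.12 could have more in total.

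**The case against.** The strongest reply is that the protocol already contains the right rule. Sections 3.3.2.2 and 3.6.1.2 permit the 100 mg/h start and do not require it, so staff can obey them and section 9.1.5.4.1 together by starting at 50 mg/h. Both sections also point to section 9.1 as a whole, which contains the administration procedures. Premedication, reaction management under section 3.4.1.1, escalation as tolerated, and the withholding of dose-dense rituximab from hypersensitive patients under section 3.6 all narrow the consequence. The first-infusion schedule itself reaches 100 mg/h after 30 minutes if nothing goes wrong. The fix would also carry over a notion of good tolerance that section 9.1.5.4.1 leaves to clinical judgement.

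Much of this stands as a limit on weight. The four-fold ratio in Step 4 does not measure the inconsistency: after a reaction at 50 mg/h, the correct 50 mg/h start is already twice the 25 mg/h restart rate. The figure of up to 20% of fatal reactions is not tied to an earlier reaction or to a starting rate. Nor do the documents show that the two-day interval adds risk. Appendix 9 contradicts nothing.

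The conflict itself remains. None of the safeguards sets the next starting rate, and the pointer to section 9.1 is placed where a reader would take it to concern dilution. A reader who relies on the dosing section alone is told that a start is allowed which section 9.1.5.4.1 excludes for this patient.

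**Conclusion.** The concern holds. For a patient who tolerated the first infusion poorly, sections 3.3.2.2 and 3.6.1.2 permit a 100 mg/h start where section 9.1.5.4.1 directs 50 mg/h. The measure of the inconsistency is that two-fold rate: 25 mg more in the first 30 minutes, which is 3.3% to 4.2% of the dose (25/750 to 25/600) at the assumed body surface area of 1.6 to 2.0 m².

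The finding rests on the current text of the sections and on no assumption about how often reactions occur, which the documents do not report. The actual harm cannot be quantified from them. It is a safety inconsistency of minor to moderate weight that should be corrected. Design, sample size, power and the primary analysis are unaffected.

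**What to change.** In both section 3.3.2.2 and section 3.6.1.2, add to the later-infusion sentence: *if the first infusion was well tolerated; otherwise follow the first-infusion schedule (section 9.1.5.3)*. Leave section 9.1.5.4.1 as it is. Appendix 9 states no rate and needs no correction once section 3.3.2.2 carries the condition.

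The cost is one clause in each of two sections, plus a longer infusion for patients who tolerated the first one poorly. With full escalation and the assumed doses of 600 to 750 mg, the slower schedule takes about 3.2 to 3.6 hours against 2.25 to 2.6 hours, roughly one hour more. The actual time depends on how far each patient can be escalated.
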